#### 4.2. Secondary Objectives

*The secondary objectives of this study are:*

1. *Estimate VE of PCV13 for pneumococcal pneumonia or pneumonia with unspecified causes among PLWH  $\geq 18$  years of age, overall and, if feasible, at 3, 5, and 7 years of follow-up*
2. *Estimate VE of PCV13 for pneumonia with unspecified causes among PLWH  $\geq 18$  years of age, overall and, if feasible, at 3, 5, and 7 years of follow-up.*

### 5. RESEARCH METHODS

#### 5.1. Study Design

*The VE study will be a retrospective cohort study using health care administrative claims and laboratory data.*

*PLWH will be identified using administrative claims and include individuals with at least one inpatient International Classification of Diseases, Ninth Revision, Clinical Modification (ICD-9-CM) or International Classification of Diseases, Tenth Revision, Clinical Modification (ICD-10-CM) code related to HIV (Appendix Table 7.1) or at least 2 outpatient ICD-9-CM or ICD-10-CM codes at least 30 days, but no more than 730 days, apart during January 1, 2014 and December 31, 2021. PLWH are required to have at least six months of continuous enrollment in one or more health plans and pharmacy benefits after their first HIV-related ICD-9-CM or ICD-10-CM code. These six months of continuous enrollment will be considered the baseline period, during which baseline covariates including demographics, comorbidities, and preventative care will be measured. The baseline period was also selected to minimize the number of outcome events that existing prior to or triggered an HIV diagnosis.*

*The date following the last date of the baseline period will be defined as the index date. The end of the study will occur on the last date that administrative claims data will be available, September 30, 2022.*

## **5.2. Study Population**

PLWH will be identified by ICD-9-CM or ICD-10-CM diagnosis codes (Appendix Table 7.1). Information provided by Komodo Health indicated that approximately 175,000 individuals meet the eligibility criteria.

All PLWH in the provided Komodo Health who meet the following criteria will be included in the analysis.

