9.5. Study Size

The planned analyses do not involve hypothesis testing and sample size calculations are not applicable. However, we examined the precision of PCV13 vaccine effectiveness for IPD and all-cause pneumonia among people living with HIV at 36 months and 97 months (which was the maximum follow-up time available from feasibility assessments) after index (Table 2 and Table 3). Komodo Health provided the following information for the precision estimates:

- 175,000 individuals had ≥ 1 inpatient or ≥ 2 outpatient HIV ICD-9-CM or ICD-10-CM code diagnosis codes between January 1, 2014 and December 31, 2021
- 56,000 (32%) of these individuals received PCV13 after their first HIV diagnosis code

The following assumptions regarding incidence and PCV13 VE for IPD and all-cause pneumonia were used:

- IPD incidence among PLWH is 183 cases per 100,000 population [28]
- All-cause pneumonia incidence among PLWH is 5,487 cases per 100,000 population
- VE for IPD due to any serotype ranges from 7.5% to 22.5%
 - Published VE estimates for vaccine type IPD range from 25% to 75% [20]. Because one-third of the adult IPD burden is considered PCV13 type [29], we multiplied this range by 30% to arrive at 7.5% to 22.5%
- VE for all-cause pneumonia ranges from 5% to 15% [30]
- Annual censoring of individuals due to loss to follow-up or death may range between 4% or 10%

Survival and censoring times were simulated assuming exponential distributions. Vaccination status was modelled as a time-varying covariate [31]. Hazard ratios were assumed as $1 - (VE/100)$. Simulations were run 100 to 200 times per scenario. Cox regression models were run on each simulated dataset to estimate the 95% confidence

PFIZER CONFIDENTIAL

intervals (CI) for the log HRs. Means were generated and exponentiated to obtain the 95% CIs for the VEs using $(1 - HR) \times 100$ and used to describe VE precision.

Table 2. Precision of PCV13 vaccine effectiveness estimates for invasive pneumococcal disease

Hypothesized Vaccine Effectiveness (%)	36 months of follow-up			97 months of follow-up		
	Lower 95% confidence interval estimate	Upper 95% confidence interval estimate	Total number of events	Lower 95% confidence interval estimate	Upper 95% confidence interval estimate	Total number of events
Scenario #1 – 4% annual censoring						
7.5	-12	25	837	-5	19	1492
22.5	3	37	817	11	33	1452
Scenario #2 – 10% annual censoring						
7.5	-15	25	766	-6	21	1272
22.5	2	38	752	9	33	1224

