### **5.2.1. Inclusion Criteria**

- 1. HIV infection defined as at least one inpatient International Classification of Diseases, Ninth Revision, Clinical Modification (ICD-9-CM) or International Classification of Diseases, Tenth Revision, Clinical Modification (ICD-10-CM) code related to HIV (Appendix Table 7.1) or ≥2 outpatient ICD-9-CM or ICD-10-CM codes at least 30 days, but no more than 730 days, apart during January 1, 2014 and December 31, 2021*

*AND*

- 2. At least 18 years of age at the time of the first recording of HIV-related ICD-9-CM or ICD-10-CM code*

*AND*

- 3. At least six months of continuous enrollment in medical and pharmacy plans after the first HIV-related ICD-9-CM or ICD-10-CM code between January 1, 2014 and December 31, 2021. A gap of 30 days or less in enrollment will be allowed during this six month period.*

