### 5.2.3. Subgroups and Stratification

*Several stratified analyses will be conducted. PPSV23 is recommended for PLWH and feasibility data provided by Komodo suggest that one in four PWLH who received PCV13 during 2014-2015 also received PPSV23 within two years. Rather than censor or exclude individuals who receive PPSV23, we will calculate PCV13 VE among PWLH who have/have not received PPSV23 before and during the study period. The analysis may also be stratified by the number of PPSV23 doses, e.g. 0, 1, 2+.*

*Feasibility assessments from Komodo indicate that approximately 25% of PWLH have at least one CD4 cell count or percentage laboratory result available. Therefore, we will calculate PCV13 VE among the subset of PWLH who have a CD4 cell count during the baseline period or follow-up, and potentially stratify by CD4 category using the patient's lowest value during the study.*

*Additional VE stratifications by ART adherence during follow-up, year of HIV diagnosis, and age will be assessed for feasibility as well, as these affect patients' immune status and immune reconstitution. Due to possible waning of the VE and different lengths of follow-up by index year, VE stratification by year of HIV diagnosis will be restricted to the first 3 years of follow-up (0 to 1079 days).*

The above subgroup analyses will be conducted if there are sufficient numbers of patients/events to maintain patient de-identification (Section 5.8.3) and where the 95% confidence intervals (CI) for the VE estimates can be expected to exclude zero in the best case scenarios for the analyses, i.e. the highest expected VE estimate, the lowest expected censoring rate and at the maximum follow-up time. Table 5.1 provides precision estimates for IPD and all-cause pneumonia under different numbers of individuals available for the analysis. The following assumptions were used for the estimates:

- 32% of individuals received PCV13
- IPD incidence among PLWH is 183 cases per 100,000 population [1]
- All-cause pneumonia incidence among PLWH is 5,487 cases per 100,000 population
- VE for IPD due to any serotype is 22.5% [2, 3]
- VE for all-cause pneumonia is 15% [4]

- Annual censoring of individuals due to loss to follow-up or death is 4%
- Up to 97 months of follow-up

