Survival and censoring times were simulated assuming exponential distributions. Vaccination status was modelled as a time-varying covariate [5]. Hazard ratios were assumed as 1-(VE/100). Simulations were run 100 to 200 times per scenario. Cox regression models were run on each simulated dataset to estimate the 95% CIs for the log HRs. Means were generated and exponentiated to obtain the 95% CIs for the VEs using  $(1 - HR) \times 100$  and used to describe VE precision.

**Table 5.1 Precision of PCV13 Vaccine Effectiveness Estimates for Invasive Pneumococcal Disease and All-Cause Pneumonia Subgroup Analyses**

Number of individuals	IPD VE: 22.5%		All-cause pneumonia VE: 15%	
	Lower 95% confidence interval estimate	Upper 95% confidence interval estimate	Lower 95% confidence interval estimate	Upper 95% confidence interval estimate
87,000 (N/2)	6%	37%	11%	18%
58,000 (N/3)	1%	40%	11%	19%
43,000 (N/4)	-5%	41%	10%	20%
35,000 (N/5)	-6%	44%	9%	20%
29,000 (N/6)	-9%	46%	9%	20%
22,000 (N/8)	-16%	49%	8%	21%

Table 5.1 shows that, under the current assumptions, 95% CIs for the IPD VE would still be expected to exclude 0% in subgroups with 58,000 individuals. For all-cause pneumonia the 95% CIs for the VE would still be expected to exclude 0 in subgroups with fewer than 22,000 individuals. Therefore, the study should have sufficient precision to address the study the objectives in several of the planned subgroups.

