## 5.6. Sample Size and Power Calculations

*The planned analyses do not involve hypothesis testing and sample size calculations are not applicable. However, we examined the precision of PCV13 vaccine effectiveness for IPD and all-cause pneumonia among people living with HIV at 36 months and 97 months (which was the maximum follow-up time available from feasibility assessments) after index. This was conducted for the 175,000 individuals expected in the overall analysis (Protocol Section 9.5) and for varying potential subgroup sizes (Section 5.2.3).*

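### SAP Table 5.1 screens IPD subgroups with 97-month precision from a Cox model described without weights, so its 58,000 figure does not apply to the strata cut at 3 years

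*SAP*

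**What the plan says.** SAP 5.2.3 makes each subgroup analysis conditional on patient counts and on the 95% CI for VE being expected to exclude zero in a best case: highest expected VE, lowest censoring, maximum follow-up. Table 5.1 supplies the precision for that decision, with up to 97 months of follow-up, and the SAP reads from it that "95% CIs for the IPD VE would still be expected to exclude 0% in subgroups with 58,000 individuals". It concludes that precision is sufficient in several of the planned subgroups.

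On the simulation behind the table, the SAP says "Cox regression models were run on each simulated dataset to estimate the 95% CIs for the log HRs", with vaccination as a time-varying covariate. It mentions no weights. SAP 5.8.7 takes the adjusted VE from marginal structural Cox models with IPT and IPT*IPC weights and cluster-robust errors.

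SAP 5.2.3 also says that VE by year of HIV diagnosis is "restricted to the first 3 years of follow-up (0 to 1079 days"). SAP Table 5.3 divides year of diagnosis into four groups.

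On the starting count, Protocol 9.5 says "175,000 individuals had ≥ 1 inpatient or ≥ 2 outpatient HIV ICD-9-CM or ICD-10-CM code diagnosis codes" in 2014 to 2021. SAP 5.2 says of the same number that "approximately 175,000 individuals meet the eligibility criteria", and SAP 5.6 says "This was conducted for the 175,000 individuals expected in the overall analysis". The inclusion criteria add an age limit, a 30-to-730-day spacing of outpatient codes and "At least six months of continuous enrollment in medical and pharmacy plans after the first HIV-related ICD-9-CM or ICD-10-CM code"; the exclusion criterion removes people with earlier PCV13.

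**The concern.** Table 5.1 decides which IPD subgroups are analysed, so its conditions should match those analyses. Two do not. Strata that stop at day 1079 cannot accrue 97 months of events, and a simulation without weights carries no allowance for variance that the weights add. Either mismatch could let an IPD subgroup through that fails the SAP's own criterion. If the 175,000 was also counted before the eligibility filters, the subgroups would be smaller than planned. What is at stake is a set of wide IPD intervals reported under a claim of sufficient precision; no estimate is biased by this.

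**Working it through.** **Inputs.** Protocol Table 2, VE 22.5%, 4% annual censoring, N = 175,000: CI 3% to 37% at 36 months and 11% to 33% at 97 months. SAP Table 5.1, IPD columns.

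**Formulas.** SE(log HR) = [ln(1 - lower) - ln(1 - upper)] / 3.92. For a subgroup of n, SE × √(175,000/n). CI for VE = 1 - 0.775 × exp(±1.96 SE). The lower limit is zero when SE = -ln(0.775)/1.96 = 0.130.

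- 97 months: ln(0.89/0.67)/3.92 = 0.0724
- 36 months: ln(0.97/0.63)/3.92 = 0.1101

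**Reproducing Table 5.1 (97 months).**

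| n | Recomputed | Printed |
|---|---|---|
| 87,000 | 5.2% to 36.6% | 6% to 37% |
| 58,000 | 0.8% to 39.4% | 1% to 40% |
| 43,000 | -3.2% to 41.8% | -5% to 41% |
| 35,000 | -6.5% to 43.6% | -6% to 44% |
| 29,000 | -9.8% to 45.3% | -9% to 46% |
| 22,000 | -15.7% to 48.1% | -16% to 49% |

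Every row agrees within 2 points, so the table is sound on its own terms and the scaling can be used.

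**Three-year strata (36 months).**

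- 87,000 (N/2): SE 0.156, CI about -5% to 43%
- 58,000 (N/3): SE 0.191, CI about -13% to 47%
- 43,750 (average of four strata, 175,000/4): SE 0.220, CI about -19% to 50%
- Break-even: 175,000 × (0.1101/0.130)² ≈ 125,000. Rounding of the printed limits allows SE 0.1068 to 0.1134, or about 118,000 to 133,000.

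Two strata of 125,000 would exceed 175,000, so at most one of the four could pass. The 36-month row averages over all index years; a stratum with fuller follow-up would do somewhat better and a late one worse.

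**Spare variance at 58,000 (97 months).** Break-even is 175,000 × (0.0724/0.130)² ≈ 54,300 from Table 2. The printed N/3 row gives SE = ln(0.99/0.60)/3.92 = 0.1278 and break-even ≈ 56,000. The margin is 58,000/54,300 = 1.07 or 58,000/56,000 = 1.04. Rounding in Table 2 alone allows a break-even of 49,400 to 59,400, so the margin cannot be told from zero.

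**Weighting.** The documents give no variance inflation, so these values are assumed. Minimum n = 54,300 × inflation: 1.1 gives about 60,000, 1.25 about 68,000, 1.5 about 81,000.

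**Starting count.** The share of the 175,000 that is eligible is also assumed. A 5% loss makes N/3 = 55,400 (lower limit about 0.3%, at break-even); 10% makes it 52,500 (-0.4%); 20% makes it 46,700 (-2.0%).

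**All-cause pneumonia (VE 15%).** Critical SE = -ln(0.85)/1.96 = 0.0829.

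- 97 months, from the 22,000 row (8% to 21%): SE 0.0389, break-even 22,000 × (0.0389/0.0829)² ≈ 4,800.
- 36 months, from Protocol Table 3 (11% to 19%): SE 0.0240, break-even 175,000 × (0.0240/0.0829)² ≈ 14,700. With an assumed inflation of 1.5 this is about 22,000, the smallest size tabulated.

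**The case against.** The screen is openly a best case, there is no hypothesis test or power target, and a borderline subgroup would simply show a wide interval. That stands for VE, censoring and the follow-up of subgroups that run to the end of the data. It does not reach weighting, which the best case does not mention, or the year strata, whose maximum follow-up is three years by the SAP's own rule. An average year stratum and the 25% CD4 subset (each about 43,750) already fail for IPD in Table 5.1, where 43,000 gives -5%. The mismatch therefore bites only for a year stratum between about 58,000 and 125,000, and the documents do not give stratum sizes.

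On weights, the SAP uses stabilized weights that may be truncated, and robust errors for split records do not by themselves widen a first-event interval. The widening is likely, but its size is unknown.

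A reader might go further, and the documents do not support it:

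- That the 175,000 is proven to be a count before the filters. Protocol 9.5 reads that way, and the amendment table lists no recount in that section when the enrollment rules changed, but SAP 5.2 says the opposite. Silence about a filter does not show that it was not applied.
- That losing people moves the 58,000. That figure is a number of analysed people at given rates. A loss changes which subgroups reach it, not the figure, unless follow-up or vaccine uptake changes too.
- That 58,000 is a fixed cutoff with no margin. It is the smallest tabulated size that passes, with a margin of about 4-7%.
- That all the precision tables ignore 36 months. Protocol Tables 2 and 3 have that column; only SAP Table 5.1 lacks it.

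**Conclusion.** The precision statement is wrong as written for the year-of-diagnosis strata in IPD. The size needed there is about 125,000 (118,000 to 133,000 with rounding), not 58,000. This rests on the protocol's own 36-month row, VE 22.5%, 4% censoring, and scaling of the SE with √n.

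At 97 months the 58,000 figure is reproduced but fragile: on the central estimates an inflation above about 1.04 to 1.07 puts zero inside the expected interval. Inflation factors and eligibility losses are assumptions, not figures from the documents. The description of the 175,000 is an unreconciled conflict between the protocol and the SAP, not a demonstrated overcount. The problem is confined to IPD.

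**What to change.** 1. Add a 36-month IPD version of SAP Table 5.1 and apply it to the year-of-diagnosis strata.
2. Re-run the IPD rows of Table 5.1, and Protocol Table 2, with the count left after all eligibility criteria and a stated allowance for weight variance. SAP 5.8.4 derives the weights without looking at their effect on VE, so the allowance can be set before VE is seen. One plus the squared coefficient of variation of the weights is a possible approximation, to be labelled as such for time-varying weights.
3. Restate the 58,000 sentence as the smallest tabulated size that passes at 97 months under the stated assumptions, and say that it does not apply to three-year strata.
4. Reconcile Protocol 9.5 with SAP 5.2 and 5.6 by stating which filters the 175,000 had passed.

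Protocol Table 3 need not be re-run. The cost is a re-run of an existing simulation and a few sentences. The downside is less favourable printed precision and possibly fewer IPD subgroups.

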### **5.2.1. Inclusion Criteria**

- 1. HIV infection defined as at least one inpatient International Classification of Diseases, Ninth Revision, Clinical Modification (ICD-9-CM) or International Classification of Diseases, Tenth Revision, Clinical Modification (ICD-10-CM) code related to HIV (Appendix Table 7.1) or ≥2 outpatient ICD-9-CM or ICD-10-CM codes at least 30 days, but no more than 730 days, apart during January 1, 2014 and December 31, 2021*

*AND*

- 2. At least 18 years of age at the time of the first recording of HIV-related ICD-9-CM or ICD-10-CM code*

*AND*

- 3. At least six months of continuous enrollment in medical and pharmacy plans after the first HIV-related ICD-9-CM or ICD-10-CM code between January 1, 2014 and December 31, 2021. A gap of 30 days or less in enrollment will be allowed during this six month period.*

### 5.2.2. Exclusion Criteria

*Patients meeting the following criterion will not be included in the study:*

1. *Evidence of PCV13 vaccination before the first HIV-related ICD-9-CM or ICD-10-CM code*

All available data prior to first HIV-related ICD-9-CM or ICD-10-CM code will be used to assess evidence of PCV13 vaccination, however there is no minimum time requirement.

### 5.2.3. Subgroups and Stratification

*Several stratified analyses will be conducted. PPSV23 is recommended for PLWH and feasibility data provided by Komodo suggest that one in four PWLH who received PCV13 during 2014-2015 also received PPSV23 within two years. Rather than censor or exclude individuals who receive PPSV23, we will calculate PCV13 VE among PWLH who have/have not received PPSV23 before and during the study period. The analysis may also be stratified by the number of PPSV23 doses, e.g. 0, 1, 2+.*

*Feasibility assessments from Komodo indicate that approximately 25% of PWLH have at least one CD4 cell count or percentage laboratory result available. Therefore, we will calculate PCV13 VE among the subset of PWLH who have a CD4 cell count during the baseline period or follow-up, and potentially stratify by CD4 category using the patient's lowest value during the study.*

*Additional VE stratifications by ART adherence during follow-up, year of HIV diagnosis, and age will be assessed for feasibility as well, as these affect patients' immune status and immune reconstitution. Due to possible waning of the VE and different lengths of follow-up by index year, VE stratification by year of HIV diagnosis will be restricted to the first 3 years of follow-up (0 to 1079 days).*

The above subgroup analyses will be conducted if there are sufficient numbers of patients/events to maintain patient de-identification (Section 5.8.3) and where the 95% confidence intervals (CI) for the VE estimates can be expected to exclude zero in the best case scenarios for the analyses, i.e. the highest expected VE estimate, the lowest expected censoring rate and at the maximum follow-up time. Table 5.1 provides precision estimates for IPD and all-cause pneumonia under different numbers of individuals available for the analysis. The following assumptions were used for the estimates:

- 32% of individuals received PCV13
- IPD incidence among PLWH is 183 cases per 100,000 population [1]
- All-cause pneumonia incidence among PLWH is 5,487 cases per 100,000 population
- VE for IPD due to any serotype is 22.5% [2, 3]
- VE for all-cause pneumonia is 15% [4]

- Annual censoring of individuals due to loss to follow-up or death is 4%
- Up to 97 months of follow-up

Survival and censoring times were simulated assuming exponential distributions. Vaccination status was modelled as a time-varying covariate [5]. Hazard ratios were assumed as 1-(VE/100). Simulations were run 100 to 200 times per scenario. Cox regression models were run on each simulated dataset to estimate the 95% CIs for the log HRs. Means were generated and exponentiated to obtain the 95% CIs for the VEs using  $(1 - HR) \times 100$  and used to describe VE precision.

**Table 5.1 Precision of PCV13 Vaccine Effectiveness Estimates for Invasive Pneumococcal Disease and All-Cause Pneumonia Subgroup Analyses**

Number of individuals	IPD VE: 22.5%		All-cause pneumonia VE: 15%	
	Lower 95% confidence interval estimate	Upper 95% confidence interval estimate	Lower 95% confidence interval estimate	Upper 95% confidence interval estimate
87,000 (N/2)	6%	37%	11%	18%
58,000 (N/3)	1%	40%	11%	19%
43,000 (N/4)	-5%	41%	10%	20%
35,000 (N/5)	-6%	44%	9%	20%
29,000 (N/6)	-9%	46%	9%	20%
22,000 (N/8)	-16%	49%	8%	21%

Table 5.1 shows that, under the current assumptions, 95% CIs for the IPD VE would still be expected to exclude 0% in subgroups with 58,000 individuals. For all-cause pneumonia the 95% CIs for the VE would still be expected to exclude 0 in subgroups with fewer than 22,000 individuals. Therefore, the study should have sufficient precision to address the study the objectives in several of the planned subgroups.

